	

• The number and percentage of subjects SARS CoV-2 seronegative at baseline for whom a seroconversion is observed will be summarized and presented at each blood sampling time point after baseline with exact 95% CI. Seroconversion is defined as detectable antibodies in the serum [<math>\geq</math> lower limit of quantification (LLOQ)].

 
Data will be presented after each vaccine dose.
 
Missing Data/Discontinuation
 
Concentration values of RBD and neutralizing antibodies marked as below the lower limit of quantification (LLOQ) will be set to 0.5*LLOQ. No imputation of missing values will be performed for any analysis (except the imputation for missing partial dates of AEs and concomitant medication).
 
Currently no replacement of discontinued or withdrawn subjects is foreseen. This plan may be affected if an important percentage of subjects opt to receive any of the authorized/licensed COVID-19 vaccines, in which case enrollment of additional subjects into this trial will be considered.

--	---

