Statistical Analyses:	
Analysis of Demographics and Other Baseline Characteristics Data will be summarized with respect to demographic characteristics (age, gender), medical history and all safety measurements using descriptive statistics (quantitative data) and contingency tables (qualitative data). Medical history will only be listed. Subjects will be stratified (post-hoc) by pre-defined co-morbidities. Subjects with multiple co-morbidities will contribute to the different corresponding strata.
 
Primary Safety Analyses
 
Solicited AEs: The number and percentage of subjects with at least 1 solicited AE of any kind, by severity grade, for local AEs, systemic AEs, and overall, will be summarized, after the first vaccination and after the second vaccination. For subjects with more than 1 episode of the same event, the maximum severity will be used for tabulations. In addition, the frequencies and severity of each solicited AE will be summarized for each vaccination day and the following 7 days. Similar tabulations will be performed for solicited systemic AEs considered as related to the trial vaccine. The duration and severity of solicited AEs will be analyzed at subject level.
 
Unsolicited AEs: Unsolicited AEs, SAEs and AESIs will be coded using the Medical Dictionary for Regulatory Activities (MedDRA) by System Organ Class (SOC) and Preferred Term (PT). The frequency and percentage of subjects reporting these events will be tabulated at the SOC and PT levels. Additional similar tabulations will be performed to evaluate severity and relationship to the trial vaccine.
 
Primary Immunogenicity Analysis The following analyses will be done for SARS-CoV-2 RBD of the S protein antibody concentrations and for neutralizing antibodies titers:
 

• Geometric mean concentrations (GMC) / GMT by group will be summarized with their 95% credibility interval at each blood sampling time point for all evaluable subjects and then separately in subjects seronegative at baseline and in subjects seropositive at baseline.

• The fold change from baseline will be computed for seropositive subjects at baseline and geometric mean of the fold change (GMFC) by group will be displayed with their 95% CI at each blood sampling time point after baseline.

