#### 10.3.5.2 Primary Immunogenicity Analysis

No formal hypothesis on immunogenicity will be tested. Descriptive statistics for the immunogenicity endpoints will be provided.

The following analyses will be done for SARS-CoV-2 RBD of the S protein antibody concentrations and for neutralizing antibodies titers:

- Geometric mean concentrations (GMC) / GMT by group will be summarized with their 95% CI at each blood sampling time point for all evaluable subjects and then separately in subjects seronegative at baseline and in subjects seropositive at baseline.
- The fold change from baseline will be computed for seropositive subjects at baseline and geometric mean of the fold change (GMFC) by group will be displayed with their 95% CI at each blood sampling time point after baseline.
- The number and percentage of subjects SARS-CoV-2 seronegative at baseline for whom a seroconversion is observed will be summarized and presented at each blood sampling time point after baseline with exact 95% CI. Seroconversion is defined as detectable antibodies in the serum [ $\geq$  lower limit of quantification (LLOQ)].

Concentrations/titers marked as below the LLOQ will be arbitrary replaced by half of the LLOQ for GMC/GMT and GMFC computations purpose.

The analyses of CMI in terms of induction by the vaccine of SARS-CoV-2 S protein-specific T-cell responses will be detailed in the SAP.

Additional immunogenicity analyses including graphs will be described in the SAP as applicable.

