
On Day 43:
 
The proportion of subjects seroconverting for SARS-CoV-2 S protein RBD antibodies, as measured by an immunoassay.
 
Individual SARS-CoV-2 S protein RBD-specific antibody levels in serum, as measured by an immunoassay.
 
Geometric mean titers (GMTs) of serum SARS-CoV-2 S protein RBD antibodies, as measured by an immunoassay.
 
In a subset of subjects*: the proportion of subjects seroconverting for SARS-CoV-2 neutralizing antibodies, as measured by an activity assay.
 
In a subset of subjects*: individual SARS-CoV-2 neutralizing antibody levels in serum, as measured by an activity assay.
 
In a subset of subjects*: GMTs of serum SARS-CoV-2 neutralizing antibodies, as measured by an activity assay.
	
In subjects who received dose 1 and dose 2 of trial vaccine and for whom the baseline blood sample for immunogenicity assessment and day 43 are available for analysis and no major protocol deviations expected to impact the immunogenicity outcomes. Subjects receiving an authorized/licensed vaccine during the course of the trial will be censored at the day after receiving the authorized/licensed vaccine. The primary immunogenicity will be analyzed with the per protocol immunogenicity subset.
 
Estimate of subjects seroconverted (SARS-CoV-2 spike protein-specific antibodies) with 95% credibility interval using prior beta (1.9, 0.1)
 
Number and percentage with exact 95% confidence intervals of subjects for who a seroconversion is observed (SARS-CoV-2 spike protein-specific antibodies)
 
Geometric mean of Fold Change from baseline with 95% CI of SARS-CoV-2 spike protein antibodies
 
Estimate of subjects seroconverted (SARS-CoV-2 neutralizing antibody levels in serum) with 95% credibility interval using prior beta(1.9, 0.1)
 
Number and percentage with exact 95% confidence intervals of subjects for who a seroconversion is observed (SARS-CoV-2 neutralizing antibody levels in serum)
 
Geometric mean of Fold Change from baseline with 95% CI of SARS-CoV-2 neutralizing antibody levels in serum

Secondary Immunogenicity	

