10.2 Fold Change from Baseline

Unless otherwise noted, fold change from baseline is defined as the ratio:

Post-baseline value/baseline value

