10.5 Missing Data

In general, no imputation of missing values will be done except for the following:

- For SARS-CoV-2 RBD of S protein antibodies, and viral neutralizing antibodies, concentration values marked as below the lower limit of quantification (LLOQ) will be set to 0.5*LLOQ for computation purposes.
- Imputation of (partially) missing AE start dates:
 - If start date year value is missing, the date uncertainty is too high to impute a rational date. Therefore, if year value is missing, the imputed AE start date is set to missing.
 - If start date year value is before the vaccination start date year value, then the AE started before the vaccination. Therefore:
 - If month is missing, the imputed start date is set to the mid-year point (i.e., 01JULYYYY).
 - If month is not missing, the imputed start date is set to the mid-month point (i.e., 15MONYYYY).
 - If start date year value is equal to the vaccination start date year value, the start date month needs to be compared against the vaccination start date month, to determine the imputation rule to apply. Therefore:
 - If month is missing, the imputed month and imputed day is the same as start of vaccination
 - If month is lower than vaccination start date month and start date day is missing, the imputed start date is set to the mid-month point (i.e. 15MONYYYY).
 - If month is equal to the vaccination start date month and start date day is missing, the start day will be set to the start day of vaccination.
 - If month is greater than the vaccination start date month and start date day is missing, the imputed start date is set to the beginning of the month (i.e., 01MONYYYY).
 - If start date year value is greater than the vaccination start date year value, the AE started after vaccination. Therefore:
 - If month is missing, the imputed start date is set to the year start point (i.e., 01JANYYYY).
 - If start date month is not missing and start date day is missing, the imputed start date is set to the beginning of the month (i.e., 01MONYYYY).
 - If after imputation of start and resolution date (see below) a start date is after the resolution date (for example if a missing day of a start date is set to 15 and the resolution date is before the 15th of the same month and year) then the start date will be set to the resolution date.
- Imputation of (partially) missing AE end dates:

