12.7.2 Primary and secondary Humoral Immune Response Endpoints

The primary humoral response endpoints will be analyzed with the per protocol immunogenicity subset population. The primary endpoint is subjects with seroconversion on day 43 compared to baseline (Day 1); the time points day 29, day 120 will be presented for the per protocol immunogenicity subset population as well. Seroconversion is defined as an increase above 1 from baseline (Day 1) (see Section 10.8.1), In addition conversion over 2 fold and 4 fold will be presented. Analysis based on the immunogenicity set will not be presented according to the abbreviated scope.

The following tables will be presented for SARS-CoV-2 S (RBD) protein antibodies, as measured by ELISA and SARS-CoV-2 neutralizing antibodies, as measured by an activity assay:

- The estimate and 95%-credibility intervals and proportion and Clopper-Pearson exact confidence intervals will be presented as well for seroconverted subjects.
- Geometric mean (GM), geometric standard deviation (GSD) and 95%- confidence intervals as well as fold change from baseline.

In addition, the following figures will be presented for the time points day 29, day 43, day 120, and for the per protocol immunogenicity population and immunogenicity set:

- Fold change from baseline for Individual subjects by co-morbidity presented in a line plot.
- Mean fold change from baseline by co-morbidity
- Individual line plots of GMTs by co-morbidity
- Line plot of GMTs with geometric mean and confidence intervals by co-morbidity
- Boxplots with median, Q1 and Q3, and whiskers representing minimum and maximum.

SARS-CoV-2 S (RBD) protein antibodies, and SARS-CoV-2 neutralizing antibodies results will be listed as well.

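### The SAP drops the protocol's restriction of fold change to baseline-seropositive subjects without declaring it, so the GMFC as written depends on the half-LLOQ constant and on each co-morbidity row's serostatus mix

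*Protocol*

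**What the plan says.** **Protocol.** The synopsis states the population for fold change ("The fold change from baseline will be computed for seropositive subjects at baseline"), and section 10.3.5.2 repeats it ("The fold change from baseline will be computed for seropositive subjects at baseline and geometric mean of the fold change (GMFC) by group"). Both places also ask for geometric mean concentrations or titres in all evaluable subjects and then separately by baseline serostatus, and both confine seroconversion to baseline-seronegative subjects. Section 10.3.5.2 adds that results below LLOQ "will be arbitrary replaced by half of the LLOQ for GMC/GMT and GMFC computations purpose".

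**SAP.** Section 10.2 gives a general ratio of post-baseline to baseline value ("Unless otherwise noted, fold change from baseline is defined as the ratio") with no serostatus condition. Section 9.4 lists, under both primary and secondary immunogenicity, "Geometric mean of Fold Change from baseline with 95% CI of SARS-CoV-2 spike protein antibodies" and the matching entry for neutralizing antibodies. The populations named there are the per protocol immunogenicity subset (PPI) and the immunogenicity set, again without a serostatus condition. Section 12.7.2 plans "Geometric mean (GM), geometric standard deviation (GSD) and 95%- confidence intervals as well as fold change from baseline", and its fold-change figures are by co-morbidity. Section 10.5 sets the substitution rule: "concentration values marked as below the lower limit of quantification (LLOQ) will be set to 0.5*LLOQ for computation purposes". No table or figure title in Appendix 4 mentions baseline serostatus.

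**What is declared.** The SAP change history records the new seroconversion definition, which now applies whatever the baseline serostatus. Sections 6.3 and 6.4 list other departures. None of the three mentions the population for the GMFC or the loss of the serostatus split for titres.

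**The concern.** In a subject with a quantifiable baseline, fold change is a measured rise. In a subject below LLOQ at baseline who responds, the denominator is 0.5*LLOQ, so fold change equals 2 × titre/LLOQ: the post-vaccination titre rescaled by a constant that the protocol itself calls arbitrary. The protocol's restriction largely keeps these two quantities apart. The SAP as written averages them.

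Two things follow. The size of the GMFC depends on the substitution constant. And the value in a co-morbidity row depends on how many of its subjects were seropositive at baseline, even where subjects of the same serostatus respond identically. All objectives are to be analysed overall and per co-morbidity, and the GMFC is the only estimand for titre magnitude that SAP 9.4 sets against the GMT endpoint. Because the split of titres by serostatus is also gone, no planned summary title shows a reader how to separate the two groups; the individual titre listings remain.

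**Working it through.** Neither document states a GMFC, an LLOQ or a baseline seropositive share, so there is no figure of the plan to reproduce. The check is algebraic, with assumed shares.

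**Inputs.** From the documents: substitution at 0.5*LLOQ (SAP 10.5); fold change as post/baseline (SAP 10.2); 129 subjects enrolled (SAP 6.3) across seven co-morbidities, with subjects contributing to every stratum that applies (SAP 12.0). Assumed: the shares and responses below. Eligibility (protocol 6.2) excludes prior SARS-CoV-2 vaccination and confirmed COVID-19 within six months. This suggests that most subjects are seronegative, but older or undiagnosed infection can enter.

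**Step 1: formula.** Let
- q = share below LLOQ at baseline;
- r = share of those who become quantifiable;
- P = their post-baseline geometric mean in LLOQ units;
- c = substitution constant in LLOQ units;
- F⁺ = GMFC in subjects quantifiable at baseline (assumed quantifiable afterwards too).

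A subject below LLOQ at both times has fold change c/c = 1 whatever c is. Hence

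ln(GMFC) = q·r·[ln P − ln c] + (1 − q)·ln F⁺

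**Step 2: the constant.** Moving c from 0.5 to 1 multiplies the GMFC by (0.5/1)^(q·r), that is, divides it by 2^(q·r):

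| q | all respond (r = 1) | half respond (r = 0.5) |
|---|---|---|
| 0.25 | 1.19 | 1.09 |
| 0.50 | 1.41 | 1.19 |
| 0.75 | 1.68 | 1.30 |
| 0.80 | 1.74 | 1.32 |
| 0.90 | 1.87 | 1.37 |
| 1.00 | 2.00 | 1.41 |

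At q = 0 the divisor is 1.00. The protocol's restriction achieves this if every subject called seropositive has a quantifiable baseline in the assay analysed.

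**Step 3: the serostatus mix.** Take seronegative to mean below LLOQ, and write F⁻ for the GMFC in that group with c = 0.5. Then GMFC = (F⁻)^q × (F⁺)^(1−q). Two rows with the same F⁻ and F⁺ but shares q₁ and q₂ differ by the ratio (F⁻/F⁺)^(q₁−q₂).

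- Shares 0.95 and 0.70, exponent 0.25: F⁻ = 50 and F⁺ = 5 give 10^0.25 = 1.78; F⁻ = 10 and F⁺ = 100 give 0.1^0.25 = 0.56.
- Shares 0.90 and 0.60, exponent 0.30: F⁻ = 20 and F⁺ = 3 give 16.5 against 9.4, a ratio of 1.77. The pair 10 and 5 gives 2^0.30 = 1.23, and the pair 30 and 2 gives 15^0.30 = 2.25.

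In every one of these examples the serostatus-specific responses are identical in the two rows.

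**The case against.** **The SAP never says that it pools.** This is correct. It pools by omission: section 10.2 is a general definition, section 6.0 says the SAP is read together with the protocol, and the table shells are a separate document. The explicit wording about ignoring baseline serostatus concerns seroconversion. A reader should not infer a stated decision to pool. Still, an estimand defined for the whole PPI, with no condition in the methods text and no split in any output title, will naturally be programmed on all subjects.

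**A reader might infer that most of the GMFC rests on imputed baselines.** The documents give no share, so this remains an assumption. Likewise 2^q is a ceiling, because subjects who stay below LLOQ contribute a ratio of 1 under any constant.

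**A reader might take baseline ≥ LLOQ to be the protocol's meaning of seropositive.** The protocol uses LLOQ to define seroconversion and gives no assay or threshold for baseline serostatus; SAP 10.8.1 measures previous exposure by N protein. An N-positive subject could have an RBD or neutralizing value below LLOQ, so the protocol's restriction alone does not guarantee a measured baseline.

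**The consequence is limited.** An all-subject GMFC is still a mean log change, no test is planned, titres are tabulated and listed, and GMFC is not itself a protocol endpoint. If two rows have equal q·r, the constant cancels between them. The protocol's own titre summary in all evaluable subjects has the same mix effect. All of this stands. However, the protocol sets that summary beside a split by serostatus, which the SAP drops.

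**Conclusion.** The discrepancy is real and undeclared. Applied as written, the SAP makes the GMFC depend on the substitution constant whenever some subjects move from below to above LLOQ, and on the serostatus mix of each row whenever the two serostatus groups respond differently. The constant can change the value by up to a factor of 2.00; at an assumed 80% below LLOQ the factor is 1.32 to 1.74, depending on how many respond. The mix can produce differences between rows in either direction: about 0.56 to 1.78 for assumed shares of 0.95 and 0.70, and up to 2.25 for 0.90 and 0.60. These sizes rest on assumed shares and responses, since the documents supply none. The matter is one of interpretation and of agreement between protocol and SAP in a descriptive analysis. It does not invalidate the immunogenicity results, and the documents do not show that the GMFC is mostly an artefact of imputation.

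**What to change.** In SAP 9.4, 10.2 and 12.7.2, and in Tables 14.2.2.1 and 14.2.4.1 and the fold-change figures:

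1. Define baseline serostatus by assay and threshold, for example a baseline at or above the LLOQ of the assay being analysed. State this as a SAP definition and do not attribute it to the protocol.
2. Report GMFC with 95% CI in baseline-seropositive subjects, as the protocol plans.
3. Report geometric mean titres with CI by baseline serostatus, and give N per group in every co-morbidity row and overall.
4. If an all-subject GMFC is kept, label it supportive, repeat it with LLOQ as the substituted value, and record the departure from the protocol in SAP 6.3 or 6.4.

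The cost is SAP wording and one by-variable in outputs already planned, with no new data. The drawback is that few of the 129 subjects may be seropositive. Their GMFC will then have wide intervals, and in some strata a listing may be all that is sensible.

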## 2 SCHEDULE OF ACTIVITIES

**Table 1 Schedule of Trial Assessments and Procedures**

	Screening	Vaccination Period										Follow-up		End of Trial
		1	2	3	Safety contact a	Phone contact	4	5	6	7	8	9	Phone contact	
Visit Number	1													10
Visit Window (days)	-7/+0	n/a	-0/+0 q	-0/+7	-2/+4	-3/+14	-0/+0 q	-2/+4	-2/+4	-2/+4	-2/+4	-7/+7	-7/+7	-0/+30
Trial Day	-7	1	2	9	15	29	30	43	57	120	211	302	393	
Signed informed consent b	X													
Inclusion/exclusion criteria b	X	X				X								
Demographics	X													
Medical history	X													
Review of criteria for delay or cancellation of vaccination c		X					X							
Investigational vaccine administration (including 1 hour observation)		X					X							
Physical examination d	X	X e				X								X
Symptom-directed physical examination		(X) e	X					X	X	X				
Vital signs d	X	X f	X				X f	X	X	X				X
ECG	X													
Diary dispensation / (re)training g	X	X	X				X	X	X					
Diary review g		X	X	X			X	X	X	X				
Solicited AEs collected by diary g	X h	X	X	X			X	X						
Unsolicited AEs collected by diary g	X h	X	X	X			X	X	X	X				
SAEs i	X	X	X	X	X	X	X	X	X	X	X	X	X	X
Intercurrent medical conditions i	X	X	X	X	X	X	X	X	X	X	X	X	X	X
AEs leading to vaccine withdrawal or trial discontinuation i		X	X	X	X	X	X	X	X	X	X	X	X	X
AESIs i		X	X	X	X	X	X	X	X	X	X	X	X	X
Concomitant medication/vaccination	X	X j	X	X	X	X	X	X	X	X	X	X	X	X

	Screening	Vaccination Period										Follow-up		End of Trial
		1	2	3	Safety contact a	Phone contact	4	5	6	7	8	9	Phone contact	10
Visit Number	1	2	3	-0/+0 q	-0/+7	-2/+4	-3/+14	-0/+0 q	-2/+4	-2/+4	-2/+4	-7/+7	-7/+7	-0/+30
Visit Window (days)	-7/+0	n/a	-0/+0 q	-0/+7	-2/+4	-3/+14	-0/+0 q	-2/+4	-2/+4	-2/+4	-2/+4	-7/+7	-7/+7	-0/+30
Trial Day	-7	1	2	9	15	29	30	43	57	120	211	302	393	
Safety laboratory (~8 mL) k - 50 subjects per co-morbidity	X	X o	X			X o	X	(X) l	X	(X) l				
Serum pregnancy test (~3 mL) m	X													
Urine pregnancy test m		X				X								
Nasopharyngeal swab collection for rapid diagnosis on site and PCR testing n								(X) n						
Binding antibody to RBD of S (spike) protein of SARS-CoV-2 (~4mL blood)		X o				X o		X		X	X		X	
Binding antibody to the N (nucleocapsid) protein of SARS-CoV-2 (~4 mL blood)		X o						X		X			X	
Subset of 25 subjects per co-morbidity: SARS-CoV-2 neutralizing activity (6 mL blood) p		X o				X o		X		X	X		X	
Subset of 25 subjects per co-morbidity: Cell-mediated immunity (3 mL) p		X o				X o		X		X				
Maximum total blood volume (mL)	~8	~25	~8	-	-	~21	~8	~17	~8	~17	~10	-	~14	
Trial end													X	

AE: adverse event; AESI: adverse event of special interest; ECG: electrocardiogram; PCR: polymerase chain reaction; RBD: receptor-binding domain; SAE: serious adverse event.

- The safety contact is only applicable for the first 25 subjects enrolled in the co-morbidities chronic kidney disease, COPD, chronic cardiovascular disease and diabetes mellitus to collect diary card data. The safety/reactogenicity data entered in the week after the first vaccination (i.e. all data recorded until Day 8 inclusively) has to be received by site and entered into EDC as soon as possible. The site and the subject should agree on the best way to transfer this data. It can be done via different means such as a site visit, phone call or a transfer of the diary to site.
- Procedures to establish subject eligibility will be performed within 7 days prior to trial vaccine administration along with consent collection and physical examinations and paper diary training. Eligibility criteria need to be reviewed on the day of vaccination prior to trial vaccine administration.
- See Section 6.4 for an overview of the criteria leading to delay or cancellation of vaccine administration. In case of delay, the vaccination should take place within the allowed time windows. The reasons for delay or cancellation should be documented in the eCRF.
- Physical examination and vital signs must be performed/measured by a qualified healthcare professional. See Section 9.1.4 for an overview of the required assessments.
- If results of a complete physical examination performed within 7 days prior to trial vaccine administration are available and sufficient in view of the protocol requirements, a symptom-directed physical examination should be performed on the day of vaccination prior to trial vaccine administration.
- Vital signs will be measured pre- and post-vaccination prior to discharge. Subjects will be observed for 1 hour following each vaccination. Vital signs must be within normal or clinically non-relevant abnormal ranges or have returned to pre-vaccination values for the subject to be discharged.
- Solicited and unsolicited AEs will be recorded in diaries. Diaries will be dispensed at Visit 1, Visit 2 and Visit 4.
- Subjects should complete the diary card for solicited systemic AEs as well as unsolicited AEs on a daily basis as of Day -7 (i.e., during 1 week before the first vaccination) to give an indication of their normal life with co-morbidities.

- i. SAEs, AESIs (including COVID-19), intercurrent medical conditions that may affect the immune response to vaccination, and AEs leading to vaccine withdrawal or trial discontinuation will be collected throughout the trial.
- j. Immunosuppressants or other immune-modifying drugs, with the exception of topically-applied, inhaled, or intranasal steroids, taken within 6 months prior to enrollment and any other medication/vaccination taken within 1 month prior to enrollment should be recorded to establish eligibility and any exception if relevant.
- k. Safety laboratory testing will be performed in the first 50 subjects enrolled and vaccinated from each co-morbidity. See Appendix 3 for an overview of the safety laboratory assessments.
- l. At Visit 6 and Visit 8 the safety laboratory only needs to be done if the previous result was abnormal.
- m. A blood sample for serum pregnancy testing will be taken from women of childbearing potential at screening to establish eligibility. Urine pregnancy tests will be performed before each vaccination, unless the serum pregnancy test was performed less than 3 days before and yielded a negative result.
- n. Swabs for COVID-19 testing will be collected in case the subject displays symptoms of acute respiratory infection (including, but not limited to COVID-19) (see Section 9.3).
- o. Blood samples on Day 1 and Day 29 must be collected prior to vaccination.
- p. This will include 12 subjects for each co-morbidity condition enrolled as part of the first 25 cases and 13 subjects enrolled as part of the next 25 subjects for each co-morbidity.
- q. In case a subject cannot come to site on the day after the vaccination due to vaccination reactions/side effects it is acceptable to conduct this visit within a window of +2 days.

Total blood volume taken is approximately 136 mL in the subset of subjects participating in the immunological assessments and the safety laboratory testing, separated over 10 times.

